9 STATISTICAL METHODS OF ANALYSIS

9.1 General Principles

Descriptive statistics will be used to summarize baseline demographic and disease characteristics, study drug administration, efficacy and safety outcomes. Descriptive summaries of discrete data will present the sample size and the incidence as a frequency and as a percentage. Descriptive summaries of continuous data will present

the sample size, group mean, standard deviation (SD), median, and range. Confidence intervals (CIs) may be included as appropriate.

Summary tables will be presented by disease types: CLL/SLL, MCL, WM, FL, GCB DLBCL, MM, non-GCB DLBCL, RICHTER's and Other (include unclassifiable DLBCL, double hit lymphoma, FL with transformation, mediastinal DLBCL, mediastinal gray zone lymphoma, non-hodgkin's lymphoma [NHL], non-mediastinal gray zone lymphoma, red pulp small B-cell lymphoma, triple hit high grade NHL, hodgkin's lymphoma, marginal zone lymphoma), unless otherwise stated.

9.2 Subject Accountability

Subject disposition will be summarized for all treated subjects including the following information:

- Subject status on acalabrutinib and pembrolizumab
- Count and reason separately for acalabrutinib and pembrolizumab discontinuation
- Subject status for the study
- Count and reason for study termination
- Time on study
- Number of death

9.3 Important Protocol Deviations

Important Protocol Deviations (IPDs) categories are defined and managed by the study team during the IPD reviews throughout the study before database lock. These definitions of IPD categories, sub-category codes and descriptions will be used during the course of the study. The final IPD list is used to produce the summary of IPDs table and the list of subjects with IPDs.

The listing of the final IPD will be provided.

9.4 Baseline Data

Summaries of demographics and baseline characteristics will be presented for subjects in the all treated population. For continuous variables, mean, standard deviation, median, minimum, and maximum will be provided. For categorical variables, number and percentage of subjects in each category will be summarized.

9.4.1 Demographics

- Sex (Male, Female)
- Age (continuous)
- Age category (≥ 65)
- Ethnicity
- Race

9.4.2 Baseline Characteristics

- Height (cm)
- Weight (kg)
- ECOG performance status at baseline
- Bulky disease (grouped as ≥ 5 and ≥ 10 cm)
- Baseline B-symptoms (weight loss, fever and night sweats)
- Baseline Rai stage (CLL/SLL)
- Baseline Ann Arbor stage

9.5 Treatment and Medications

9.5.1 Prior Anticancer Therapies

A prior anticancer therapy is defined as a systemic therapy subjects received, either as a single or combination therapy, for the treatment of active corresponding target disease with a start and end date occurring before the date of first dose of study treatment.

Therapies given as a consolidation or maintenance of a response or remission will not be considered as a separate regimen. The number of lines and type of prior therapy will be summarized according to each disease cohort.

9.5.2 Prior and Concomitant Medications Received for Indications Other than Target Disease

Data reported on concomitant CRF page will be used. Medications started or ended prior to first dose will be considered as prior treatment. Concomitant therapy is defined as all medications used on or after the first dose, through the treatment phase, and for 30 days following the last dose of study drug. Using this definition, a medication can be classified as both prior and concomitant. Start date and end date will be imputed based on the rules provided in Section **12.1.** of the SAP. Medications with completely missing start and stop dates will be considered as concomitant medications.

Prior and concomitant medications other than antineoplastic agents or other systemic therapies after enrollment will be summarized by the World Health Organization (WHO) Drug Dictionary therapeutic class, pharmacological class, and preferred term by each disease area.

9.5.3 Exposure to Study Drug

Descriptive statistics (n, mean, standard deviation, median, and range) will be used to summarize regarding the number of acalabrutinib doses prescribed:

- Total number of doses taken
- Duration of exposure (the interval between first dose date and last dose date)
- Average daily dose (the ratio of total dose administered and treatment duration)
- Relative dose intensities (the ratio of average daily dose and prescribed doses)
- The number and timing of prescribed dose reductions and interruptions

Descriptive statistics (n, mean, standard deviation, median, and range) will be used to summarize regarding the number of acalabrutinib doses prescribed:

- Total number of doses taken
- Duration of exposure (the interval between first dose date and last dose date)
- Average dose per cycle (total dose administered per cycle)
- Relative dose intensities (the ratio of average daily dose and prescribed doses)
- The number and timing of prescribed dose reductions and interruptions
-

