# 3.5 STUDY DRUG DOSING

Acalabrutinib 100 mg BID will be orally administered. Pembrolizumab 200 mg will be administered every 3 weeks by IV infusion. In Part 3, subjects with MF will receive a run-in of 6 weeks with acalabrutinib alone (100 mg BID). Subjects who are demonstrating a clinically meaningful response, in the opinion of the investigator, may continue on acalabrutinib monotherapy; those who are not will receive combination therapy with acalabrutinib (100 mg BID) and pembrolizumab (200 mg Q3W) as described above.

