## 3.6 DURATION OF THERAPY

Subjects may continue to receive acalabrutinib treatment until disease progression or an unacceptable drug-related toxicity occurs as defined in the protocol. Treatment with acalabrutinib can continue until the end of trial, defined as 48 months after the last subject is enrolled. Subjects who are still on treatment at the end of the study and deriving clinical benefit from acalabrutinib treatment may continue treatment. At the time of the final data cutoff and database closure, subjects who remain in this study may be transitioned to a separate rollover study or remain within this study for continued access to study drug. Once all active subjects are eligible to continue to receive acalabrutinib and after database closure, this study would be considered closed. There will be no further data collection other than reporting of SAEs (see Section 6.2). Access within this study will enable continued treatment with visit assessments per standard of care, whereas the separate rollover study will enable treatment continuation with visit assessments and data collection per the rollover study protocol.

Treatment with pembrolizumab may continue for 24 months (103 weeks) from first dose of pembrolizumab provided subjects are tolerating the drug and not progressing. In addition, pembrolizumab treatment can end for subjects with confirmed CR (or sCR for MM) if treatment has been administered for at least 24 weeks and 2 doses of pembrolizumab have been administered after confirmation of CR/sCR. Subjects who have **confirmed** 

progressive disease will come off treatment. Note: If there is uncertainty regarding whether there is cancer progression, the subject may continue study treatment and remain under close observation (e.g., evaluated at 4- to 8-week intervals) pending confirmation of progression. In particular, transient worsening of disease during temporary interruption of study therapy (e.g., for drug-related toxicity or intercurrent illness) may not indicate disease progression. In such circumstances, and if medically appropriate, subjects may resume therapy and relevant clinical, laboratory, and/or radiographic assessments should be done to document whether tumor control can be maintained or whether actual disease progression has occurred.

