# 5.5.3 Study Treatment Administration and Compliance

Descriptive information will be provided regarding the number of acalabrutinib and pembrolizumab doses prescribed, the total number of doses taken, the number of days of treatment, and the number and timing of prescribed dose reductions and interruptions.

For each subject, acalabrutinib and pembrolizumab compliance will be described in terms of the relative dose intensity.

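### SAP 9.5.3 specifies exposure for acalabrutinib twice and for pembrolizumab not at all, and its relative dose intensity rule does not return 100% for a fully compliant 3-weekly infusion on either reading of the denominator

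*SAP*

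**What the plan says.** Protocol 5.5.3 covers both drugs: "For each subject, acalabrutinib and pembrolizumab compliance will be described in terms of the relative dose intensity". It also asks, for both, for doses prescribed and taken, days of treatment, and reductions and interruptions.

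SAP 9.5.3 delivers this in two bulleted blocks with the same lead-in. Each says that descriptive statistics "will be used to summarize regarding the number of acalabrutinib doses prescribed". Pembrolizumab is not named anywhere in the section.

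The blocks differ in one line. The first has "Average daily dose (the ratio of total dose administered and treatment duration"); the second has "Average dose per cycle (total dose administered per cycle") in its place. The other lines are the same in both, including "Duration of exposure (the interval between first dose date and last dose date") and "Relative dose intensities (the ratio of average daily dose and prescribed doses").

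SAP section 10 reports no major departure from the protocol's analyses. SAP 9.2 does summarise status and discontinuation separately for the two drugs.

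**The concern.** Read literally, one of the two study drugs has no exposure analysis although the protocol requires one. The per-cycle line suggests that the second block was meant for pembrolizumab, so the natural repair is to change the drug name there.

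That repair leaves an RDI line built for a drug taken every day. The second block uses an average daily dose that it does not define. The stated interval ends on the date of the last dose, which loses almost nothing for a twice-daily capsule but loses a whole 3-week dosing interval for an infusion. The prescribed dose in the denominator has no unit, so it could be per day, per infusion or in total. Two programmers following the same text could report very different pembrolizumab RDIs for the same subject, and neither would show a compliant subject as compliant.

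**Working it through.** The documents give no RDI figure, so there is none to reproduce. The check applies the SAP rule to pembrolizumab at the protocol's schedule.

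**Inputs**
- Schedule: "Pembrolizumab 200 mg will be administered every 3 weeks by IV infusion" (Protocol 3.5). Per day this is 200/21 = 9.52 mg.
- Longest course: "Treatment with pembrolizumab may continue for 24 months (103 weeks) from first dose of pembrolizumab" (Protocol 3.6). Infusions at Weeks 1, 4, …, 103 number (103 − 1)/3 + 1 = 35.
- Duration: last dose date minus first dose date (SAP 9.5.3). For k infusions on schedule this is 21(k − 1) days. The SAP does not say whether a day is added, so both counts are shown.

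**Full compliance**

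Total dose is 200k mg, so the average daily dose is 200k/[21(k − 1)].
- Denominator 200/21 mg per day: RDI = k/(k − 1), or 21k/[21(k − 1) + 1] with one day added.
- Denominator 200 mg: RDI = k/[21(k − 1)].

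| Infusions k | Interval, days | Per-day denominator | Same, +1 day | 200 mg denominator |
|---|---|---|---|---|
| 1 | 0 | undefined | 2100% | undefined |
| 2 | 21 | 200% | 190.9% | 9.5% |
| 5 | 84 | 125% | 123.5% | 6.0% |
| 10 | 189 | 111.1% | 110.5% | 5.3% |
| 35 | 714 | 102.9% | 102.8% | 4.9% |

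The correct value in every row is 100%.

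**One missed infusion**

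Suppose 5 of 6 scheduled infusions are given, including the last. The interval is 21 × 5 = 105 days and the total is 1000 mg. With the per-day denominator, RDI = (1000/105)/(200/21) = 100%, or 105/106 = 99.1% with one day added. The share actually delivered is 5/6 = 83.3%.

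**Proposed definition** (mg received divided by 200 mg × scheduled infusions from first to last dose, inclusive)
- Full compliance: 200k/(200k) = 100% for every k, including k = 1.
- 5 of 6: 1000/1200 = 83.3%.

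**Acalabrutinib**, 100 mg twice daily for 28 days, prescribed dose taken as 200 mg per day
- SAP interval of 27 days: (5600/27)/200 = 103.7%.
- With one day added: (5600/28)/200 = 100%.

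**The case against.** The strongest reply is that this is a double copying slip. The second block replaces the daily average with a per-cycle average, so its RDI line may simply be left over from the first block. If RDI were the average dose per cycle divided by 200 mg, with a cycle taken as one 3-week slot, full compliance would score 100% and 5 of 6 would score (1000/6)/200 = 83%. That is a sensible intention, but the SAP does not state it. The RDI line still refers to a daily dose, and 9.5.3 does not define a cycle. The reply therefore supports rewriting the line as well as the drug name.

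Four stronger readings are tempting, and the documents do not support them:

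- **The formula exceeds 100%.** This requires the second block to be pembrolizumab, the treatment duration to be the first-to-last-dose interval, and the denominator to be per day. The SAP states none of these, and with a 200 mg denominator the error goes the other way. The 2100% for a single infusion also depends on an added day; on the stated interval the value is undefined.
- **Missed infusions would be hidden.** Only the RDI would miss them. The same block lists total doses taken and the number and timing of reductions and interruptions, and Protocol 5.5.3 asks for doses prescribed as well as taken.
- **Most subjects fall where the distortion is large.** Protocol 1.4.2.1 gives a median exposure of 3.4 months at a 2017 cutoff without saying which drug. If it applied to pembrolizumab, it would mean about 5 to 6 infusions, but that is an assumption, and a median does not show a majority below an undefined threshold.
- **The primary safety objective is undermined.** RDI is not among the safety endpoints in SAP 4.1, and SAP 9.7.1 does not adjust adverse events for exposure.

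**Conclusion.** The point holds in a limited form. The omission of pembrolizumab from SAP 9.5.3 is plain on the page and conflicts with Protocol 5.5.3. Putting the right drug name in the second block would still leave a rule that fails for a 3-weekly infusion: a compliant subject with 5 infusions would score about 124% or 125% on one reading and 6% on the other.

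The size depends on course length. On the per-day reading the excess is 25 percentage points at 5 infusions, 11 at 10 and about 3 at 35. These figures assume that the second block is meant for pembrolizumab, that infusions are on schedule, and that the treatment duration is the first-to-last-dose interval. The direction of the error depends on the unstated unit. The failure to give 100% for full compliance does not.

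The consequence is confined to a protocol-required descriptive summary. SAP section 5 plans no formal hypothesis test, and neither an endpoint nor the expansion rules use RDI. It should be corrected because it would put an uninterpretable compliance figure into the report.

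**What to change.** In SAP 9.5.3:

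1. Name pembrolizumab in the lead-in of the second block.
2. Replace its RDI line with one definition: total mg received divided by (200 mg × number of scheduled 3-weekly infusions from first to last dose, inclusive).
3. For acalabrutinib, keep the daily-dose formula, set duration to last dose date − first dose date + 1, and state the prescribed dose in mg per day.

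Use only the slot-counting definition for pembrolizumab. A version based on last dose − first dose + 21 days agrees only when infusions fall exactly on schedule, and Protocol Appendix 5 allows ±3 days. With 5 infusions and the last one 3 days late, the slot count gives 100% and the day count gives 5 × 21/108 = 97%. Infusions not given after the last one received are outside this ratio; they belong with the discontinuation summary in SAP 9.2.

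The cost is a few lines of SAP wording and one derivation, with no new data and no change to trial conduct. If the SAP is not reissued, its Introduction already provides for recording changes of method in the clinical study report.

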9.6 Analyses of Efficacy Endpoints

9.6.1 Response Rate

9.6.1.1 Definition

ORR will be defined as the proportion of subjects who achieve a response defined in Section 4.2 in protocol for different disease. For lymphoma, response means partial response (PR) or better, for WM subjects response means minor response (MR) or better, for subjects with MF, response including clinical improvement or better (clinical improvement, PR, or CR). Please refer to Protocol section 4.2 for the detail information and definition of the response.

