### 4.2 INVESTIGATOR'S ASSESSMENT OF RESPONSE TO TREATMENT

The investigator must rate the response of the subjects as outlined below:

- NHL, Hodgkin lymphoma, or RS refer to Table 5
- CLL/SLL refer to Table 6
- WM refer to Table 7
- MM refer to Table 8
- MF refer to Table 9

Response and Site	PET-CT-Based Response	CT-Based Response	
Complete	Complete metabolic response Complete radiologic resp (all of the following)		
lymphatic sites a residual mass on 5PS+ must regress to ≤1		Target nodes/nodal masses must regress to ≤1.5 cm in LDi No extralymphatic sites of disease	
Nonmeasured lesion	Not applicable	Absent	
Organ enlargement	Not applicable	Regress to normal	
New lesions	None	None	
Bone marrow	No evidence of FDG-avid disease in the marrow	Normal by morphology; if indeterminate, IHC negative	
Partial	Partial metabolic response	Partial remission (all of the following)	
Lymph nodes and extra lymphatic sites	Score 4 or 5+ with reduced uptake compared with baseline and residual mass(es) of any size At interim, these findings suggest responding disease	
 
≥50% decrease in SPD of up to 6 target measurable nodes and extranodal sites
 
When a lesion is too small to measure on CT, assign
 
	
	At end of treatment, these findings indicate residual disease	5 mm×5 mm as the default value When no longer visible, 0 mm×0 mm For a node >5 mm×5 mm, but smaller than the normal, use actual measurement for calculation	
Nonmeasured lesions	Not applicable	Absent/normal, regressed, but no increase	

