Partial response (PR)	
 
Monoclonal IgM protein is detectable
 
≥50% but <90% reduction in serum monoclonal IgM level from baseline a
 
Reduction in extramedullary disease i.e., lymphadenopathy/splenomegaly if present at baseline
 
No new signs for symptoms of active disease
 

Minor response (MR)	
 
Monoclonal IgM protein is detectable
 
≥25% but <50% reduction in serum monoclonal IgM level from baseline a
 
No new signs for symptoms of active disease
 

Stable disease (SD)	
 
Monoclonal IgM protein is detectable
 
<25% reduction and <25% increase in serum monoclonal IgM level from baseline*
 
No progression in extramedullary disease i.e., lymphadenopathy/splenomegaly
 
No new signs for symptoms of active disease
 

Progressive disease	
 
≥25% increase in serum IgM level a from lowest nadir (requires confirmation on ≥2 consecutive measurements at least 4 weeks apart).
 
AND
 
Progression of clinical features attributable to the disease per Owen 2013.
 

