#### Owen 2013.

IgM=immunoglobulin M; WM=Waldenström macroglobulinemia.

a Sequential changes in IgM levels may be determined either by M protein quantitation or total serum IgM quantitation by nephelometry.

Response Subcategory	Response Criteria a	
Complete response (CR)	
 
Negative immunofixation on the serum and urine and
 
	
	Disappearance of any soft tissue plasmacytomas and	
	
 
<5% plasma cells in bone marrowb.
 
	
Stringent complete response (sCR)	CR as defined above plus	
response (SCR)	Normal FLC ratio and	
	Absence of clonal cells in bone marrow b by immunohistochemistry or immunofluorescence c .	
Near complete response (nCR)	
 
Meeting the criteria for CR, except that the persistence of original monoclonal protein by immunofixation while absence of monoclonal protein on serum or urine protein electrophoresis.
 
	
Very good partial response (VGPR)	
 
Serum and urine M-component detectable by immunofixation but not on electrophoresis or
 
	
	
 
≥90% reduction in serum M-component plus urine M-component
 
<100 mg/24 h.
 
	
Partial response (PR)	
 
≥50% reduction of serum M-protein and reduction in 24-h urinary M-protein by ≥90% or to <200 mg/24 h
 
	
	
 
If the serum and urine M-protein are unmeasurable at baseline, a ≥50% decrease in the difference between involved and uninvolved FLC levels is required in place of the M-protein criteria
 
	
	
 
If serum and urine M-protein are unmeasurable at baseline, and serum free light assay is also unmeasurable, ≥50% reduction in plasma cells is required in place of M-protein, provided baseline bone marrow plasma cell percentage was ≥30%
 
	
	
 
In addition to the above listed criteria, if present at baseline, a ≥50% reduction in the size of soft tissue plasmacytomas is also required
 
	
Minor response (MR)	• MR includes subjects in whom some, but not all, criteria for PR are fulfilled providing the remaining criteria satisfy the requirements for MR.	

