# 5.5.4 Analysis of Efficacy Parameters

#### **Response Rate**

The individual and composite endpoints of response and progression will be determined. Tumor control will be documented at each assessment by response category (see Section 4.2) as defined for each response parameter, date that response is first documented, and date of disease progression.

ORR will be defined as the proportion of subjects who achieve a response of PR or CR (see Section 4.2). For Part 3 subjects with MF, ORR will be defined as the proportion of subjects who achieve a response of clinical improvement or better (clinical improvement, PR, or CR) as shown in Table 9. ORR will be calculated and the corresponding exact 2-sided 90% and 95% CIs will be derived.

In addition, for subjects with CLL/SLL in Parts 1 and 2, a response will be assessed according to Table 6, which reflects modified International Working Group response criteria (Hallek 2008) as recently updated (Cheson 2012) to include PRL. For the purpose of this analysis, lymphocytosis at a given timepoint will be defined as absolute lymphocyte count which is above normal limits and is not ≥50% decreased from baseline.

For Part 3 subjects with MF, an additional analysis will evaluate response when defined as CR + PR only. A descriptive analysis will be done on the subgroups of subjects with MF who receive acalabrutinib alone or the combination of acalabrutinib and pembrolizumab.

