9.6.1.2 Analysis Methods

The primary analysis of ORR will be conducted on the all treated population. A descriptive analysis will be done on for subgroups of subjects who receive acalabrutinib alone or the combination of acalabrutinib and pembrolizumab. ORR and the corresponding 90% and 95% two-sided CI calculated using exact method to the binomial distribution will be presented.

The number and proportion of subjects within each category of response as well as the associated 95% CIs will be presented. The proportion will be estimated by dividing the number of subjects within each category of response by the total number of subjects in the analysis population. Each subject will be counted within only one response group, with the best response during the study as the classification group.

In addition, for subjects with CLL/SLL in Parts 1 and 2, a response will be assessed according to Table 4-2, which reflects modified International Working Group response criteria (Hallek 2008) as recently updated (Cheson 2012) to include PRL. For the purpose of this analysis, lymphocytosis at a given timepoint will be defined as absolute lymphocyte count which is above normal limits and is not \geq 50% decreased from baseline. For Part 3 subjects with MF, an additional analysis will evaluate response when defined as CR + PR only.

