10 CHANGES FROM PROTOCOL-SPECIFIED ANALYSES

There is no major change from protocol-specified analyses.

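### The SAP's response rate in Waldenström macroglobulinemia counts minor responses that the protocol's ORR definition leaves out, and the SAP does not list the change

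*SAP*

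**What the plan says.** **Protocol.** Section 5.5.4 gives the general definition: "ORR will be defined as the proportion of subjects who achieve a response of PR or CR (see Section 4.2"). It replaces that definition for one disease: "For Part 3 subjects with MF, ORR will be defined as the proportion of subjects who achieve a response of clinical improvement or better". The CLL/SLL text, which brings in partial response with lymphocytosis, is worded as an additional assessment. WM is not mentioned.

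Section 4.2 assigns each disease a grading table: "The investigator must rate the response of the subjects as outlined below". For WM this is Table 7, which lists CR, very good partial response (VGPR), PR, MR, stable disease and progressive disease. PR needs a fall in monoclonal IgM of at least 50%. MR needs at least 25% but less than 50%.

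**SAP.** Section 9.6.1.1 defines response by disease and refers to protocol 4.2 for the detail. Lymphoma needs PR or better, and "for WM subjects response means minor response (MR) or better". Myelofibrosis keeps clinical improvement or better, and 9.6.1.2 adds a stricter rate beside it: "For Part 3 subjects with MF, an additional analysis will evaluate response when defined as CR + PR only". WM has no matching stricter rate. Section 9.6.6 takes the responders for duration of response (DOR) from protocol 4.2. Section 10 reads: "There is no major change from protocol-specified analyses".

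**The concern.** The two documents use one name, ORR, for two different WM endpoints. The SAP's version has the lower threshold, so the direction of the difference is known in advance: its rate cannot fall below the protocol's. WM is also summarized as its own disease group (SAP 9.1), so the difference is not diluted by pooling.

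A reader of the study report who relies on Section 10 would take the WM figure to be the ORR that the protocol defines. The same question reaches DOR and the responder-only summaries in SAP 9.6.2 to 9.6.5, because the set of WM responders depends on whether MR counts. The main Kaplan-Meier analyses of PFS and OS use the All-treated Population and are not affected.

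**Working it through.** **Step 1. Compare the texts for WM.**

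| Best response (Table 7) | Counts under protocol 5.5.4 | Counts under SAP 9.6.1.1 |
|---|---|---|
| CR | yes | yes |
| VGPR | yes, reading PR or CR as PR or better | yes |
| PR | yes | yes |
| MR | no | yes |
| SD, PD | no | no |

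The definitions differ in the MR row only. Protocol 4.2 does not close the gap, because it says how to grade response and not which grades enter ORR.

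**Step 2. Size of the difference.** Let n be the number of treated WM subjects, r the number with PR or better, and m the number whose best response is MR.

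- Protocol rate = r/n
- SAP rate = (r + m)/n
- Difference = m/n, which is never negative and is zero only if m = 0

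Per MR subject (m = 1):

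- n = 30, the Part 2 cap per group: 1/30 = 3.3 points
- n = 15, assumed: 1/15 = 6.7 points
- n = 10, assumed: 1/10 = 10.0 points

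**Step 3. Effect on the planned intervals.** SAP 9.6.1.2 plans exact two-sided 90% and 95% intervals. For x responders out of n, with a equal to 0.10 or 0.05:

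- lower bound = Beta quantile at a/2 with parameters x and n − x + 1
- upper bound = Beta quantile at 1 − a/2 with parameters x + 1 and n − x

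Check against the plan's own figures: at n = 30 the 90% bounds are 9.1% and 35.7% for x = 6, and 11.5% and 39.4% for x = 7 (the 11.5 is 11.499 before rounding). SAP Table 3-2 prints 9% and 36%, and 11% and 39%. They agree.

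One MR subject added (the responder counts are assumed):

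| n | Responders | Rate | 90% CI | 95% CI |
|---|---|---|---|---|
| 30 | 6 | 20.0% | 9.1–35.7% | 7.7–38.6% |
| 30 | 7 | 23.3% | 11.5–39.4% | 9.9–42.3% |
| 10 | 2 | 20.0% | 3.7–50.7% | 2.5–55.6% |
| 10 | 3 | 30.0% | 8.7–60.7% | 6.7–65.2% |

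The intervals are wide in every row. A single reclassified subject moves the point estimate visibly but changes little in what the data can exclude.

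**The case against.** **The protocol wording is shorthand.** Taken literally, PR or CR also leaves out VGPR, so 5.5.4 needs disease-specific detail, and SAP 9.6.1.1 could be seen as supplying it. This stands in part. VGPR is deeper than PR, so reading it in is natural. MR is shallower than PR, and the same logic does not reach it. Where the protocol wanted a lower threshold, for myelofibrosis, it said so.

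**The SAP is open about the rule.** The MR rule is prespecified in plain words, and 9.6.1.2 tabulates each best-response category with a 95% CI. A reader can add up PR or better and compute an interval from the count. This stands and limits the harm, but the exact 90% and 95% intervals for the protocol's own rate are not among the planned outputs.

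**Section 10 speaks only of major changes.** The sponsor may regard this one as minor. That is a fair reading, but the difference is still not recorded there.

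**Version.** The SAP was written to Amendment 6, and the supplied protocol may be later. The part of its change summary that can be read lists no change to 5.5.4. This is a caveat, not a rebuttal.

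Three stronger readings are tempting, and the documents do not support them.

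- *A reader might infer from multiple myeloma that MR was never meant to count.* Protocol Table 8 also grades MR there, and the SAP names MR as a response only for WM. But SAP 9.6.1.1 gives no explicit myeloma rule at all, so its silence shows nothing about MR.
- *A reader might infer that programmers would build conflicting WM sets for DOR.* SAP 9.6.1.1 is the SAP's only explicit WM rule and cites the same protocol section as 9.6.6. Read together, they point to MR or better. The fault is a loose cross-reference.
- *A reader might infer that the rule could carry WM past the 20% minimum ORR of interest.* That figure is a planning benchmark, and SAP Section 5 states that no formal hypothesis is tested.

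**Conclusion.** The discrepancy holds on the text: SAP 9.6.1.1 counts MR in the WM response rate, protocol 5.5.4 does not, and SAP Section 10 does not list the departure. The SAP rate equals or exceeds the protocol rate by 1/n for each WM subject with MR as best response, or 3.3 points each at n = 30.

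The documents state neither how many WM subjects were treated nor how many had MR, so the actual difference may be zero. The smaller group sizes and all responder counts in the illustration are assumptions. The conclusion also rests on reading the protocol's PR or CR as PR or better, so that VGPR is included.

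Severity is minor: ORR is secondary and descriptive, WM enrollment closed under Amendment 3, and the PR-or-better count can be recovered from the planned best-response table.

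**What to change.** 1. In SAP 9.6.1, report two WM rates under separate labels: the protocol-defined ORR (PR, VGPR or CR) with exact 90% and 95% CIs, and the MR-or-better rate. This follows what the SAP already does for myelofibrosis with its CR + PR analysis.
2. In SAP Section 10, list the MR-or-better definition for WM as a departure from protocol 5.5.4.
3. In SAP 9.6.6, replace the pointer to protocol 4.2 with an explicit statement of which WM responder set is used for DOR and the responder summaries, labelled to match the rate it accompanies. Either set can be used, provided it is named.

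The cost is one extra row in the WM response table and wording in three places, with no new data. The protocol-defined WM rate may turn out lower than the MR-or-better rate.
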